### 5.5.5 Outcome Definitions and Measurement

The study outcomes will first be defined by querying the PEDSnet CDM for clinically relevant terms associated with these outcomes including signs, symptoms, diagnoses and procedures. These data are coded using Systematized Nomenclature of Medicine-Clinical Terms (SNOMED-CT). SNOMED-CT is an international logic-based, controlled vocabulary used in clinical care that enables meaning-based retrieval of clinical information from electronic health records. SNOMED-CT is based on three types of components: (i) concepts which represent a clinical meaning and have a unique identifier, (ii) descriptions which represent labels of these concepts and (iii) relationships which are binary links between concepts that help define the meaning of each concept. SNOMED-CT has over 300,000 concepts organized according to a hierarchy rooted by 19 high-level classes or axes. Each top-level hierarchy contains sub-hierarchies that further specify a concept.

**Currently, there are no available validated algorithms to identify the study outcomes using the SNOMED-CT vocabulary.** The SNOMED-CT concepts (listed in [Table 3](#) will be reviewed and cased definitions for each outcome will be developed using appropriate algorithms that will

be developed in consultation with clinicians. Second, additional information for these outcomes will be ascertained by medical records review as indicated in Section 5.4. Additionally, the laboratory results may be included during the chart review to confirm any diagnoses. **Sensitivity analyses will be conducted to assess the impact of the case definitions on the effect estimates.**

A number of broad outcomes will be examined in this study and will include:

- Cardiac disorders
- Skin and subcutaneous tissue disorders
- Nervous system disorders
- Metabolism and nutrition disorders
- Psychiatric disorders
- Injury, poisoning and procedural complications
- General disorders and administration site conditions
- Investigations – prolonged PR on ECG
- Drug reaction with eosinophilia and systemic symptoms syndrome
- Severe cutaneous adverse reactions
- Hypersensitivity

Additionally, specific medical events under each broad category will be evaluated as listed below:

- Cardiac Disorders
  - Atrioventricular block
  - Atrioventricular block complete
  - Atrioventricular block first degree
  - Atrioventricular block second degree
  - Arrhythmia
  - Bradyarrhythmia
  - Bradycardia
  - Cardiac fibrillation

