  - Cardiac flutter
  - Tachyarrhythmia
  - Atrial fibrillation
  - Atrial flutter
  - Cardiac arrest

- 
- Torsade de pointes
  - Ventricular arrhythmia
  - Ventricular fibrillation
  - Ventricular tachyarrhythmia
  - Palpitations
  - Skin and subcutaneous tissue disorders
    - Stevens-Johnson syndrome
    - Toxic epidermal necrolysis
    - Angioedema
    - Urticaria
    - Pruritus
    - Rash
  - Nervous system disorders
    - Dizziness
    - Somnolence
    - Paresthesias
    - Loss of consciousness
    - Syncope
  - Metabolism and nutrition disorders
    - Appetite disorder
    - Decreased appetite
    - Diet refusal
    - Hypophagia
    - Food aversion
  - General disorders and administration site conditions
    - Chest pain
    - Gait disturbances
  - Injury, poisoning and procedural complication
    - Injection site discomfort
    - Injection site erythema
    - Injection site irritation
    - Injection site pain

Table 3 SNOMED-CT concepts for the study	
Study outcome	SNOMED code
Cardiac Disorders	
Atrioventricular block	SCTID: 233917008
Atrioventricular block complete	SCTID: 27885002
Atrioventricular block first degree	SCTID: 270492004
Atrioventricular block second degree	SCTID: 195042002
Cardiac Arrhythmia (disorder)	SCTID: 698247007
Nodal rhythm disorder (disorder)	SCTID: 71792006
Atrial arrhythmia (disorder)	SCTID: 17366009
Cardiac arrhythmia (disorder)	SCTID: 698247007
Atrio-ventricular node arrhythmia (disorder)	SCTID: 88412007
Neonatal dysrhythmia (disorder)	SCTID: 276513001
Electrocardiogram: sinus arrhythmia (finding)	SCTID: 427393009
Ventricular arrhythmia (disorder)	SCTID: 44103008
Premature beats (disorder)	SCTID: 29717002
Electrocardiographic ventricular arrhythmia (finding)	SCTID: 164893009
Supraventricular arrhythmia (disorder)	SCTID: 72654001
Electrocardiographic supraventricular arrhythmia (finding)	SCTID: 164887001
Bradyarrhythmia	SCTID: 421869004
Supraventricular bradyarrhythmia (disorder)	SCTID: 762534000
Bradycardia	
Electrocardiogram: bradycardia (finding)	SCTID: 426627000
Bradycardia (finding)	SCTID: 48867003
Cardiac fibrillation (disorder)	SCTID: 40593004
Ventricular fibrillation (disorder)	SCTID: 71908006
Atrial fibrillation (disorder)	SCTID: 49436004
Rapid atrial fibrillation (disorder)	SCTID: 314208002
Electrocardiographic atrial fibrillation (finding)	SCTID: 164889003

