History of urticaria (situation) (Prevalent code)	SCTID: 213325008
Dermatographic urticaria (disorder)	SCTID: 7632005
Pruritus	
Pruritic disorders (disorder)	SCTID: 279333002
Itching of skin (finding)	SCTID: 418363000
Generalized pruritus (finding)	SCTID: 276444007
Pruritus caused by drug (disorder)	SCTID: 724843002
Generalized pruritus of unknown etiology (disorder)	SCTID: 403576004
Pruritic rash (disorder)	SCTID: 64144002
Pruritus due to systemic disorder (disorder)	SCTID: 403575000
Pruritus due to neurological disorder (disorder)	SCTID: 724844008
Rash	
Eruption of skin (disorder)	SCTID: 271807003
Eruption (morphologic abnormality)	SCTID: 1806006
Eruption caused by drug (disorder)	SCTID: 28926001
Serum rash (disorder)	SCTID: 213323001
Generalized rash (disorder)	SCTID: 725119006
Localized eruption of skin (disorder)	SCTID: 724877007
On examination - rash present (situation)	SCTID: 268911002
Localized skin eruption caused by drug and medicament (disorder)	SCTID: 200893007
Pseudolymphomatous eruption caused by drug (disorder)	SCTID: 402748000
Generalized skin eruption caused by drug and medicament (disorder)	SCTID: 200892002
On examination - discoid rash (disorder)	SCTID: 164427005
On examination - mouth rash (disorder)	SCTID: 163148009
On examination - itchy rash (disorder)	SCTID: 304386008
On examination - scalp rash (disorder)	SCTID: 395122007
On examination - allergic rash (disorder)	SCTID: 275955005
On examination - erythematous rash (disorder)	SCTID: 135888007
Macular eruption (disorder)	SCTID: 271756005
Bullous eruption (disorder)	SCTID: 271759003
Macular rash (morphologic abnormality)	SCTID: 89757007
Papular rash (morphologic abnormality)	SCTID: 70831001
Pruritic rash (disorder)	SCTID: 64144002
Pustular rash (morphologic abnormality)	SCTID: 48055004
Purpuric rash (disorder)	SCTID: 284078000
Vesicular rash (morphologic abnormality)	SCTID: 53788007

Table 3 SNOMED-CT concepts for the study	
Study outcome	SNOMED code
Blistering eruption (disorder)	SCTID: 247464001
Vasculitic rash (morphologic abnormality)	SCTID: 27006004
Premycotic eruption (disorder)	SCTID: 404102002
Weal (disorder)	SCTID: 247472004
Synchronous rash (finding)	SCTID: 409642009
Morbilliform rash (morphologic abnormality)	SCTID: 50495000
Multimorphic rash (disorder)	SCTID: 301447009
Morbilliform eruption (disorder)	SCTID: 247470007
Maculopapular rash (morphologic abnormality)	SCTID: 47725002
Grade of skin rash (observable entity)	SCTID: 424223007

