Maculopapular eruption (disorder)	SCTID: 247471006
Vesiculobullous rash (morphologic abnormality)	SCTID: 14912003
Papulovesicular rash (morphologic abnormality)	SCTID: 4538007
Complaining of a rash (finding)	SCTID: 162415008
Application site rash (disorder)	SCTID: 95371007
Cutaneous hypersensitivity (disorder)	SCTID: 21626009
Nervous System disorders	
Dizziness (finding)	SCTID: 404640003
Dizziness present (situation)	SCTID: 162260006
Dizziness of unknown cause (finding)	SCTID: 429530004
Dizziness due to drug (disorder)	SCTID: 473188002
Dizziness on standing up (finding)	SCTID: 407645004
Postural dizziness (finding)	SCTID: 103017008
Dizziness and giddiness (finding)	SCTID: 271789005
Somnolence	
Drowsiness, function (observable entity)	SCTID: 79519003
Drowsy (finding)	SCTID: 271782001
Complaining of somnolence (finding)	SCTID: 272026007
Daytime somnolence (finding)	SCTID: 141000119100
Excessive somnolence (finding)	SCTID: 372947007
Disorders of excessive somnolence (disorder)	SCTID: 194439006
Somnolence syndrome (disorder)	SCTID: 370971007
Paresthesia (finding)	SCTID: 91019004
Paresthesia of upper limb (finding)	SCTID: 95673003
Facial paresthesia (finding)	SCTID: 95665007
Paresthesia of foot (finding)	SCTID: 309087008
Paresthesia of hand (finding)	SCTID: 309086004
Paresthesia of finger (finding)	SCTID: 762374005

Table 3 SNOMED-CT concepts for the study	
Study outcome	SNOMED code
Transient paresthesia (finding)	SCTID: 135873002
Circumoral paresthesia (finding)	SCTID: 1141007
Paresthesia of lower extremity (finding)	SCTID: 429783005
Paresthesia of right upper limb (finding)	SCTID: 15973701000119104
Paresthesia of right lower limb (finding)	SCTID: 15634791000119106
On examination - paresthesia present (finding)	SCTID: 163707002
Injection site paresthesia (disorder)	SCTID: 95399003
Paresthesia of left lower limb (finding)	SCTID: 15634841000119109
Paresthesia of left upper limb (finding)	SCTID: 15973661000119106
Oral paresthesia (disorder)	SCTID: 95524000
Paresthesia of mucous membrane (finding)	SCTID: 95358009
Paresthesia of tongue (disorder)	SCTID: 95527007
Numbness of skin (finding)	SCTID: 102603008
Burning sensation of skin (finding)	SCTID: 762397008
Prickling sensation of skin (finding)	SCTID: 162248005
Numbness and tingling sensation of skin (finding)	SCTID: 101000119102
Finding of sensation of skin (finding)	SCTID: 297971001
Altered sensation of skin (finding)	SCTID: 247325003

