Skin sensation disturbance (finding)	SCTID: 80910005
Complaining of paresthesia (finding)	SCTID: 31048100
Loss of consciousness	
Loss of consciousness (finding)	SCTID: 419045004
Brief loss of consciousness (finding)	SCTID: 32834005
Moderate duration loss of consciousness (finding)	SCTID: 40863000
Prolonged loss of consciousness (finding)	SCTID: 7862002
Syncope	SCTID: 271594007
Syncope and collapse (disorder)	SCTID: 309585006
Metabolism and nutrition disorders	
Appetite disorder	
Non-organic loss of appetite (disorder)	SCTID: 192017004
Appetite problem (finding)	SCTID: 289163007
Appetite symptom (finding)	SCTID: 161824009
Centrally acting appetite suppressant adverse reaction (disorder)	SCTID: 292259006
Altered appetite (finding)	SCTID: 249473004
Eating disorders management (procedure)	SCTID: 386264009
Decrease in appetite (finding)	SCTID: 64379006
Non-organic loss of appetite (disorder)	SCTID: 192017004

Table 3 SNOMED-CT concepts for the study	
Study outcome	SNOMED code
Decreased appetite Decrease in appetite (finding)	SCTID: 64379006
Diet refusal Refusing food (finding) Does not eat (finding) Unable to eat (finding)	SCTID: 105481005 SCTID: 288887001 SCTID: 288885009
Hypophagia Decrease in appetite (finding) Non-organic loss of appetite (disorder)	SCTID: 64379006 SCTID: 192017004
Food aversion Aversion to food or drink (finding) Finding of food aversion and cravings (finding) Sensory aversion to particular foods (finding) Aversion to particular food (finding)	SCTID: 248134002 SCTID: 289143000 SCTID: 16230791000119104 SCTID: 248135001
General disorders and administration site conditions	

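### Table 3 lists outcome codes whose labels do not denote an adverse event, and the protocol states no rule that removes them before the primary rates are computed

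*Protocol*

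**What the plan says.** Table 3 of Protocol Section 5.5.5 gives the SNOMED-CT concepts for each outcome. These entries are at issue:

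- Cardiac arrhythmia: "Electrocardiogram: sinus arrhythmia (finding" (427393009).
- Somnolence: "Drowsiness, function (observable entity" (79519003).
- Rash: "Grade of skin rash (observable entity" (424223007).
- Paresthesia: "Finding of sensation of skin (finding" (297971001).
- Appetite disorder: "Eating disorders management (procedure" (386264009) and "Centrally acting appetite suppressant adverse reaction (disorder" (292259006).

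Section 5.5.1 defines the primary rates and IRRs by the terms of Section 5.5.5. Section 5.9.1.2 counts only the first occurrence after the index date and ends time at risk there.

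On the status of the list, Section 5.5.5 says that the concepts "will be reviewed and cased definitions for each outcome will be developed using appropriate algorithms that will" be worked out with clinicians. It adds that no validated SNOMED-CT algorithm exists and promises sensitivity analyses of the case definitions.

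**The concern.** A code is useful as an outcome only if its presence means that something went wrong. Sinus arrhythmia on an ECG is usually normal respiratory variation in a child. An observable entity names what was assessed, not what was found, so without a value it can mean assessed and normal, or grade 0. The skin-sensation heading names no abnormality. The two appetite entries are a management procedure and a reaction attributed to a different class of drug.

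Under the first-occurrence rule such a code does two things. It turns the child into a case for that System Organ Class, and it stops the clock before any later true event in the class. The overall rate of any event of interest in Section 5.9.1.2 is affected in the same way. Because the absolute rates are themselves primary measures, the harm is not confined to the between-group comparison.

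**Working it through.** **Which primary outcomes are touched**

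| Entry | Primary outcome | How clear the problem is |
|---|---|---|
| 427393009 | Cardiac | Clear, resting on general clinical knowledge |
| 424223007 | Skin | Clear from its own label (observable, no value) |
| 79519003 | Nervous system | Clear from its own label (observable, no value) |
| 297971001 | Nervous system | Clear from its own label (no abnormality named) |
| 386264009, 292259006 | Metabolism and nutrition | Less certain |

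**Figures available.** The protocol gives no event rate, expected IRR, power or frequency of any code. Its only size figure is 875 patients in Section 5.9.3, a database count before the full criteria are applied. There is therefore no stated figure to reproduce, and everything below rests on assumed inputs.

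**Formula.** Let the comparator's true event rate be a and its non-event code rate be c. Let IRR be the true rate ratio, and r the ratio of non-event code rates, high dose to comparator. With constant rates,

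observed IRR = (IRR × a + r × c) / (a + c) = IRR × (1 − f) + r × f, where f = c / (a + c).

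f is the share of the comparator's coded events that are non-events. The comparator's absolute rate is multiplied by (a + c) / a = 1 / (1 − f).

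**Results over an assumed range of f**

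| | f = 10% | f = 20% | f = 30% | f = 50% |
|---|---|---|---|---|
| Comparator rate multiplied by | 1.11 | 1.25 | 1.43 | 2.00 |
| True IRR 2.0, r = 1 | 1.90 | 1.80 | 1.70 | 1.50 |
| True IRR 1.5, r = 1 | 1.45 | 1.40 | 1.35 | 1.25 |
| True IRR 1.0, r = 1 | 1.00 | 1.00 | 1.00 | 1.00 |
| True IRR 1.0, r = 2 | 1.10 | 1.20 | 1.30 | 1.50 |
| True IRR 1.5, r = 3 | 1.65 | 1.80 | 1.95 | 2.25 |
| True IRR 2.0, r = 2 | 2.00 | 2.00 | 2.00 | 2.00 |

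For example, at f = 20% with a true IRR of 2.0 and r = 1: 2.0 × 0.8 + 1 × 0.2 = 1.80. With a true IRR of 1.0 and r = 2: 1.0 × 0.8 + 2 × 0.2 = 1.20.

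The observed IRR is a weighted average of the true IRR and r, so it moves toward r. That means toward 1 only when r = 1. Section 5.1 assumes that loading-dose patients are more likely to be in status epilepticus. If they are also monitored and coded more often, r exceeds 1. The propensity weighting in Section 5.9.1.1 corrects this only as far as measured baseline covariates explain it.

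**Do the stated safeguards remove the codes?**

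- Review with clinicians (Section 5.5.5): it could, but no criterion for dropping a concept is stated.
- Chart review: Section 5.1 says all eligible patients, to find additional cases; Section 5.4.1 says about 10%. Section 5.9.4 relies on it to limit misclassification, but at 10% most false cases would stay.
- Sensitivity analysis (Section 5.9.1.4): it adds an outcome-related medication or procedure code, with the period still to be defined. It leaves the primary estimate unchanged.

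**The case against.** The strongest reply is that Table 3 is a candidate list. Section 5.5.5 defers the case definitions to a clinical review, Section 5.7.1 describes code-set development as part of data-quality work, and final code sets are often fixed in a later document. That stands in part. A reader might infer that the protocol already counts these codes as adverse events, and it does not go that far. But this is the only outcome list printed, and it was partly screened: the history codes for urticaria and angina are marked as prevalent, whereas these entries carry no mark. The amendments in Section 15, made during programming, do not touch Table 3.

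Second, some entries are defensible. Sections 5.1 and 5.5.5 allow procedures as query terms, and the definition in Section 7.1 needs no causal link, so a reaction to another drug can be an adverse event. This is why the two appetite entries are the less certain part. They still say little about appetite loss after IV lacosamide.

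Third, a reader might add "Unable to eat (finding" and its companion code under diet refusal, on the ground that they capture intubated or nil-by-mouth children. Nothing in the protocol shows that, and both are plausible signs of the listed outcome. Restricting them to children allowed oral feeding would need feeding status, which Table 4 does not list.

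Fourth, the planned sensitivity analysis would tend to drop benign sinus arrhythmia and unvalued observables. That is fair, but it is a secondary result with details still open.

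**Conclusion.** The point holds in a limited form. Four concepts (427393009, 79519003, 424223007 and 297971001) do not by their labels, or by general clinical knowledge for the first, denote an adverse event. Two more (386264009 and 292259006) are doubtful. All sit under terms that feed primary outcomes, and no stated rule removes them.

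If they are kept, the affected rates are too high, and the IRR is biased toward 1 under equal recording and in either direction otherwise. A reader might conclude that the IRRs are simply diluted. The protocol does not support that, because it expects the two cohorts to differ in severity.

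Nor can a definite size be claimed. The table above shows what assumed shares would do. The observables, the procedure and the other-drug reaction may be coded so rarely that they add almost nothing; sinus arrhythmia is the entry most likely to matter. The correction is worth making because the codes can be named and it is cheap.

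**What to change.** Before the outcome query is run, amend Table 3 or the case definitions that come out of its review:

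- Delete 427393009 and 297971001 from the primary case definitions.
- Count 79519003 and 424223007 only when a recorded value shows abnormality.
- Delete 386264009 and 292259006 from appetite disorder.
- Report the cardiac, skin, nervous system and metabolism outcomes on the cleaned list.
- Leave 288885009 and 288887001 under diet refusal; at most, run a sensitivity analysis without them.

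The deletions need no new data. The two observables need their recorded value, and are not counted where none exists. The downside is slightly fewer coded events. If the query has already been programmed, the edit costs a re-run.

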#### 5.4.1 Plan for data collection

The PEDSnet database consists of electronic medical records and is not an administrative claims database. It consists of both structured and unstructured data that is recorded by physicians during all health encounters that patients have in the healthcare network.

The study primary outcomes will be ascertained in two steps; i) review of coded events in the common data model (CDM) and ii) medical chart extraction which will include both coded data and free text. PEDSnet uses Systematized Nomenclature of Medicine-Clinical Terms (SNOMED-CT) to represent the diagnoses; SNOMED-CT, ICD-9, ICD-10, CPT-4 and HCPCS codes to map procedures; RxNorm for dispensed and prescribed medications; and LOINC to represent laboratory results observations. The medical charts are considered the gold standard as they contain the original source of information for the medical encounters and include free hand information that is recorded by the physician during a health encounter. Therefore, including the medical chart review in addition to using data from the CDM will ensure that all available clinical information is utilized to validate the database findings and answer any queries.

**First step:** The PEDSnet network uses SNOMED-CT to enable standardization and pooling of diagnoses data across the across the 8 health systems included in the network. Initially, data will be evaluated relating to the study outcomes using the SNOMED-CT codes in the common dataset. The data in the CDM are coded using SNOMED-CT, an international logic-based, controlled vocabulary used in clinical care that enables meaning-based retrieval of clinical information from electronic health records. SNOMED CT is the most comprehensive, multilingual clinical terminology in the world, containing more than 300,000 medical concepts (diagnoses or findings), divided into hierarchies as diverse as body structure, clinical findings, geographic location and pharmaceutical/biological product. Each concept is represented by an individual code number and several concepts can be used simultaneously to describe a complex condition, for example presenting symptoms arising from a disease. This allows for separation of symptoms of drug exposure versus a comorbid chronic condition e.g. cardiac arrhythmia. Consequently, it is expected that the data in the CDM will include detailed information on the study outcomes.

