### **5.5.2 Secondary outcome measure**

The secondary variables that will be evaluated in this study include:

- Incidence rate and incidence rate ratio of atrioventricular block
- incidence rate and incidence rate ratio of atrioventricular block complete
- incidence rate and incidence rate ratio of atrioventricular block first degree
- incidence rate and incidence rate ratio of atrioventricular block second degree
- incidence rate and incidence rate ratio of arrhythmia
- incidence rate and incidence rate ratio of bradyarrhythmia
- incidence rate and incidence rate ratio of bradycardia
- incidence rate and incidence rate ratio of cardiac fibrillation
- incidence rate and incidence rate ratio of cardiac flutter
- incidence rate and incidence rate ratio of tachyarrhythmia
- incidence rate and incidence rate ratio of atrial fibrillation
- incidence rate and incidence rate ratio of atrial flutter
- incidence rate and incidence rate ratio of cardiac arrest
- incidence rate and incidence rate ratio of torsade de pointes
- incidence rate and incidence rate ratio of ventricular arrhythmia
- incidence rate and incidence rate ratio of ventricular fibrillation
- incidence rate and incidence rate ratio of ventricular tachyarrhythmia
- incidence rate and incidence rate ratio of palpitations
- incidence rate and incidence rate ratio of chest pain
- incidence rate and incidence rate ratio of gait disturbances
- incidence rate and incidence rate ratio of injection site discomfort
- incidence rate and incidence rate ratio of injection site erythema
- incidence rate and incidence rate ratio of injection site irritation
- incidence rate and incidence rate ratio of injection site pain
- incidence rate and incidence rate ratio of stevens-johnson syndrome
- incidence rate and incidence rate ratio of toxic epidermal necrolysis
- incidence rate and incidence rate ratio of angioedema
- incidence rate and incidence rate ratio of urticaria

- incidence rate and incidence rate ratio of pruritus
- incidence rate and incidence rate ratio of rash
- incidence rate and incidence rate ratio of dizziness
- incidence rate and incidence rate ratio of somnolence
- incidence rate and incidence rate ratio of paresthesias
- incidence rate and incidence rate ratio of loss of consciousness
- incidence rate and incidence rate ratio of syncope
- incidence rate and incidence rate ratio of appetite disorder
- incidence rate and incidence rate ratio of decreased appetite

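### Table 3 prints a malformed SNOMED-CT identifier for the complaint form of paresthesia; a literal query on it would retrieve nothing for that one concept

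*Protocol*

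**What the plan says.** Section 5.5.5 of the protocol sets out how outcomes are found: "The study outcomes will first be defined by querying the PEDSnet CDM for clinically relevant terms". Table 3 in that section gives the concepts and codes. Section 5.4.1 explains why the code itself matters: "Each concept is represented by an individual code number".

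Under Nervous system disorders, the Paresthesia block of Table 3 holds 26 identifiers. The first is the general concept, "SCTID: 91019004". The last is the finding Complaining of paresthesia, printed as "SCTID: 31048100". The protocol gives no other code for that finding.

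The block feeds a named secondary variable in section 5.5.2, "incidence rate and incidence rate ratio of paresthesias". It also feeds the primary outcome Nervous system disorders in section 5.5.1.

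**The concern.** The printed number has eight digits. Comparable entries in the same table have nine, for example "Complaining of a rash (finding) SCTID: 162415008" and "On examination - paresthesia present (finding) SCTID: 163707002". Length alone proves nothing, because valid eight-digit identifiers also occur in the table. SNOMED-CT identifiers do, however, carry a built-in error check, and this one can be tested.

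If the code is wrong and the list is run as printed, the query returns no row for this concept. A patient whose paresthesia was recorded only as a complaint would then be handled as event-free. Under section 5.9.1.2 that takes one patient out of the numerator. It also lengthens the time at risk, which would otherwise stop at the first event. Both changes lower the estimated rate. Paresthesia is a reported symptom, so the complaint concept is a plausible place for it to be recorded, but the protocol does not say how often this happens.

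**Working it through.** **Inputs.** The printed identifier 31048100 and the other 278 distinct identifiers, all from Table 3. The two rules below are general properties of SNOMED-CT identifiers and are not stated in the protocol.

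**Rule 1, check digit (Verhoeff).** Read the digits from right to left. Replace the digit in position i (counting from 0) by its image under the i-th power (mod 8) of the permutation 0→1, 1→5, 2→7, 3→6, 4→2, 5→8, 6→3, 7→0, 8→9, 9→4. Combine the results in sequence with the multiplication table of the dihedral group of order 10. A valid number ends at 0.

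**Rule 2, partition.** For a concept, the two digits before the check digit must be 00 (short form) or 10 (long form). The long form carries a 7-digit namespace and so needs at least 11 digits.

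**The printed code, 31048100.**
- Digits from the right: 0, 0, 1, 8, 4, 0, 1, 3
- Permuted: 0, 1, 8, 2, 1, 4, 7, 6
- Running value: 0, 1, 9, 7, 6, 7, 0, 6. It ends at 6, so it fails Rule 1.
- The partition digits read 10, the long form, but there are only 8 digits. It fails Rule 2.

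**A control, the general concept 91019004.**
- Digits from the right: 4, 0, 0, 9, 1, 0, 1, 9
- Permuted: 4, 1, 5, 7, 4, 4, 7, 8
- Running value: 4, 0, 5, 3, 2, 1, 8, 0. It passes Rule 1, and its partition is 00.

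**The whole table.** Of 279 distinct identifiers, 278 pass both rules, and 31048100 is the only failure. All 25 other identifiers in the Paresthesia block pass. Only one of the ten possible final digits satisfies Rule 1, so 278 passes cannot be chance. The table's own contents therefore support the rules.

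**Which single lost digit would explain it?** Every digit was inserted at every position of 31048100. Nine results pass Rule 1:
- 310348100, 310458100, 310483100, 319048100, 371048100 and 631048100 have partition 10 with only 9 digits, so they fail Rule 2.
- 310481040 has partition 04 and 310481600 has partition 60, so they fail Rule 2.
- 310481001 has partition 00. Its digits from the right are 1, 0, 0, 1, 8, 4, 0, 1, 3; permuted 1, 1, 5, 9, 7, 5, 2, 0, 3; running value 1, 2, 7, 3, 5, 0, 2, 2, 0. It passes both rules.

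So 310481001 is the only well-formed number that is one digit away by insertion, and it is the printed number with a final 1 added.

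**Effect on the estimates.** Let s be the share of paresthesia patients identifiable only through this concept, and ignore the small change in person-time. The observed rate is then about (1 − s) times the rate with the concept retrieved, and the observed rate ratio is about (1 − s_high) / (1 − s_recommended) times the ratio with it retrieved. The protocol gives no value for s in either group. If s is the same in both, the ratio does not move.

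**The case against.** The case against giving this much weight is good, and most of it stands.

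- **Table 3 is not the executed query.** Section 5.5.5 says the listed concepts are to be reviewed and case definitions developed with clinicians. Section 5.7.1 describes code-set development that looks at terminology structure and, where possible, recovers missing codes from source values. Either step could catch this. Neither names a check of the identifiers, and a clinician reading labels would not see a missing digit.
- **Coded data are only the first route.** Section 5.1 plans a chart review for all eligible patients, and section 5.9.4 expects detailed nursing notes. But section 5.4.1 speaks of reviewing charts for approximately 10% of patients. Under that reading most patients rest on coded data alone.
- **The outcome is densely covered.** A patient who also carries any of the 25 other paresthesia codes is still found. A query that expands the general concept to its descendants might recover this one too, but the protocol does not specify expansion and lists narrower concepts one by one.
- **The digit may have been lost in reading the PDF.** This cannot be excluded. The Hypersensitivity rows of the same table show layout damage. Since every other identifier came through intact, including those of 17 digits, a slip in the source is the likelier explanation, but only the original page settles it.

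A reader might infer more: that paresthesia events as a whole can never be retrieved, that every patient recorded under this concept is lost, that the rates are in fact understated, or that the dose comparison is biased. The documents support none of these. One concept of 26 is affected, a loss needs at least one patient identified by that concept alone, no count is given, and nothing suggests that s differs between the dose groups.

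**Conclusion.** The printed identifier is malformed and cannot be a SNOMED-CT concept. That follows from the number itself and does not depend on knowing the right code. Queried literally, it retrieves nothing, so records carried only by this concept are missed for paresthesias and, without another listed nervous-system event, for Nervous system disorders.

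The practical effect is probably small: one of 279 distinct identifiers, and one of 26 in its block. Its size cannot be derived from the protocol, and no bias in the rate ratio is shown. This is a minor transcription correction that touches no design choice or analysis method.

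The conclusion assumes that the number on the original page is the one shown here and that no later code list has already corrected it.

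**What to change.** 1. Look at Table 3 on the original page to rule out a digit lost in reading.
2. If the page shows the same number, replace it with the identifier for this finding confirmed in the terminology release. The candidate to confirm is 310481001. The protocol does not contain it, so it should not be adopted on the check digit alone.
3. Run a check-digit test and a concept look-up, matching number to label, on all of Table 3 before the database query. The look-up also catches a valid number attached to the wrong label, which the check digit cannot.
4. Section 15 refers to amendments made while programming was under way, so check the programmed code list as well. If the wrong number was used, rerun the two affected outcomes.

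The cost is one corrected code and a few lines of programming.
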